**REGULATORY FRAMEWORK:**

Please indicate all that apply:

	DOD (Department of Defense)
	DOE (Department of Energy)
	DOJ (Department of Justice)
	ED (Department of Education)
	EPA (Environmental Protection Agency)
	FDA (Food and Drug Administration)
	HHS (Department of Health and Human Services)
	VA
	Other:

**FUNDING: Departmental sources only**

**CLINICAL TRIALS**

Is this a clinical trial per the NIH definition of a Clinical Trial?  Yes  No

NIH Definition of a Clinical Trial:

A research study in which one or more human subjects are prospectively assigned to one or more interventions. An "intervention" is defined as a manipulation of the subject or subject's environment for the purpose of modifying one or more health-related biomedical or behavioral processes and/or endpoints. Examples include: drugs/small

## Tegaderm™ Placement for Bag Mask Ventilation in the Bearded Patient

molecules/compounds; biologics; devices; procedures (e.g., surgical techniques); delivery systems (e.g., telemedicine, face-to-face interviews); strategies to change health-related behavior (e.g., diet, cognitive therapy, exercise, development of new habits); treatment strategies; prevention strategies; and, diagnostic strategies (which may include placebo or other control) to evaluate the effects of those interventions on health-related biomedical or behavioral outcomes.

**Use the following four questions to determine the difference between a clinical study and a clinical trial:**

- 1) Does the study involve human participants?  Yes  No
- 2) Are the participants prospectively assigned to an intervention?  Yes  No
- 3) Is the study designed to evaluate the effect of the intervention on the participants?  Yes  No
- 4) Is the effect being evaluated a health-related biomedical or behavioral outcome?  Yes  No

Note that if the answers to the 4 questions are yes, your study meets the NIH definition of a clinical trial, even if...

- You are studying healthy participants
- Your study does not have a comparison group (e.g., placebo or control)
- Your study is only designed to assess the pharmacokinetics, safety, and/or maximum tolerated dose of an investigational drug
- Your study is utilizing a behavioral intervention

If yes to all 4 questions, please confirm that the research team is familiar with and agrees to comply with the investigator requirement to register the study on the ClinicalTrials.gov database. Additionally, the approved consent document(s) must be uploaded to the ClinicalTrials.gov database  Yes  No

For any assistance with registration of your trial or the requirements, please contact [contact]

## 1. Objectives

- 1.1. This is a prospective randomized cross-over controlled trial intended to assess the efficacy of applying Tegaderm™ over bearded patients' circumoral area to improve bag mask ventilation after induction of general anesthesia. We will use Pneumotachography to measure our primary outcome: the amount of airway leak during mask ventilation (Tidal Volume Inspired mL –Tidal Volume Expired mL). Secondary measures include peak inspiratory pressures (PPins; cm H2O) and airway resistance (Res; cm H2O/l/sec).
- 1.2. Hypothesis: Application of Tegaderm™ over patient with circumoral facial hair will significantly improve bag mask ventilation via improvement of facemask seal.

## 2. Background

- 2.1. Bag mask ventilation (BMV) is an essential skill for health care professionals involved in airway management. This ubiquitously needed skill can be lifesaving in emergent situations but is frequently impeded by various patient characteristics. If incorrectly approached and applied, BMV may be ineffective and lead to hypoxia, hypercarbia  or pulmonary aspiration . Difficult mask ventilation (DMV) pathophysiology is well described by El-Orbany et al as having two broad components: 1) operator or technique related and 2) airway related factors. Independent risk factors for DMV include the presence of a beard, increased BMI (> 26 kg/m^2), edentulism, age >55 years, history of snoring, Mallampati III or IV, male gender, limited mandibular protrusion, and airway masses . In recent years, there has been a joint effort amongst emergency physicians, anesthesiologists, and pre-hospital clinicians to improve our understanding of BMV, standardize our approach and teach optimization with a surplus of corrective measures when faced with difficult BMV . The most basic optimizing maneuvers such as switching from a single hand to two-handed thenar-eminence grip has shown promising objective results . More novel approaches to improve facemask seal have been suggested such as keeping dentures in mouth or packing the mouth with gauze during induction of general anesthesia of the edentulous patient , and employing ergonomically designed facemasks , accessories , and intraoral masks  to reduce operator error and grip fatigue.

A common independent DMV risk factor encountered by multiple modalities of healthcare providers is the bearded airway. Bag mask ventilation in the bearded patient has many difficulties to overcome, for both the novice and expert alike. In a review of 50,000 anesthetics looking at prediction of impossible mask ventilation, the bearded patient was deemed the only modifiable independent predictor despite attempts by multiple anesthesiologists . There are multiple factors that contribute to beards as an independent risk factor for DMV. The presence of a beard decreases the ability to create an airtight seal of the face mask increasing air leakage during positive pressure ventilation by providers . Beards can also conceal architectural facial anomalies concealing other risk factors for DMV, such as men with retrognathia in attempt to alter their appearance .

## Tegaderm™ Placement for Bag Mask Ventilation in the Bearded Patient

Additionally, beards can inhibit the provider's ability to effectively grip the jaw to perform an adequate chin lift .

**2.2.** There have been multiple proposed techniques to address the management of beards. The most effective, but perhaps hardest to achieve, is shaving of the beard prior to induction . For a willing patient in a non-emergent setting this may be the most ideal intervention, but has limited compliance, and is not applicable in emergent or pre-hospital settings where time is more crucial and resources more limited. Viscous jelly to form an adequate seal at the mask-beard-skin interface has been proposed , but may further limit effective grip to perform chin lift. Use of a pediatric mask over the nose and nasopharyngeal airway with manual closure of the oral airway , which has shown promising data in maintaining upper airway patency but may not be readily translatable across multiple provider modalities. The use of cling film to wrap the face in an emergent scenario , previously noted to require significant head manipulation, potential risk for pulmonary edema, and limiting gas exchange during the intervention . The use of a supraglottic airway device may also be an appropriate intervention for DMV bearded patients, but there is limited evidence in the literature to say LMA is superior to face masks in the setting of difficult airways and a supraglottic airway is commonly an inappropriate airway device in the perioperative period .

**2.3.** A simple novel approach noted improvement of BMV in the bearded patient  by placing a large (6 x 8 inch) Tegaderm™ across the lower face to improve face-to-mask seal, after first cutting a hole in the device to permit passage of air and instruments. To date, evidence for improved facemask seal in the bearded patient has only been anecdotal. We plan on studying a heretofore non-studied technique involving application of a large Tegaderm™ across the lower face of the bearded patient to quantify its effectiveness at improving mask ventilation in this anesthetized population. This technique can be applied rapidly, without dramatic head manipulation, preserving effective grip, and can be adopted across multiple healthcare modalities, making it a worthy intervention to explore in detail. By quantifying the effectiveness of this intervention, we hope this study can be used to inform guidelines for the management of difficult BMV in the bearded patient.

### 3. Study Design

- 3.1. Our study design is a randomized prospective crossover trial in adult patients (>18 years), with circumferential perioral facial hair longer than 5 mm who will undergo elective non-cardiac surgery in the main adult operating rooms of the University of New Mexico Hospital.
- 3.2. Allocation concealment: Providers and subjects will be blinded to which method they will start with (control versus intervention) via envelope method prior to induction of general anesthesia.
- 3.3. Subjects who are consented to participate in the study will have facial hair measured as a continuous variable length (mm).
- 3.4. Mask ventilation operators will be confined to anesthesiology residents, anesthesiologist assistants (AA), and AA students all of whom are familiar with bag mask ventilation. Mask ventilation will occur using a two-handed Thenar-Eminence (TE) grip without the addition of an oropharyngeal airway. All operators will be instructed on how to perform this technique prior to patient enrollment. We will use Pressure Control ventilation mode on Anesthesia Ventilator machine (Dräger Perseus A500) set at 10 breaths per minute, I:E time of 1:2 and peak inspiratory pressure of 20 cm H2O, all of which are routine in our practice and within typical ranges at the national level. These are specified only in order to reduce practice variation not related to the intervention itself. An external pneumotachograph device and sensors (Phillips Respironics NM3™ respiratory profile monitor; Respironics CAPNOSTAT® Mainstream CO2 sensor) will be used to measure ventilation parameters ( Vtins; mL, VtExp; mL, PPins; cm H2O, Res; cm H2O/L/sec) with collected data electronically saved to a dedicated flash drive associated with the pneumotachograph .

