## **9. Resources Available**

*9.1. Investigator qualifications:*

PI [name] MD is a board-certified anesthesiologist, Division Chief of Cardiac Anesthesiology and Professor at UNM. Other investigators include experienced clinicians, a PhD research specialist, and medical residents; all investigators' research duties are well within their usual job duties. All research procedures will be performed by personnel who have appropriate training, experience, and authorization.

*9.2. Medical decision-makers:*

All clinical decisions will be made by appropriate providers who are duly authorized and credentialed to do so.

*9.3. Other resources:*

- UNM's operating rooms handle a high caseload, and the investigators anticipate little difficulty in recruiting 60 relevant patients from among them in one calendar year.
- Engagement in research activities is an expected part of all investigators' job duties, so conducting this study is not anticipated to conflict with their clinical, scientific, or administrative duties.
- The UNM surgical suites are equipped with the personnel, supplies, and equipment necessary to respond to any eventuality that may arise as a result of participation in this study.

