## Tegaderm™ Placement for Bag Mask Ventilation in the Bearded Patient

After obtaining informed written consent, patients will be pre-medicated with 1–2 mg of midazolam prior to entry into the operating room. Subjects will be transferred to the operating room table where they will lie in the supine position with the head and neck placed in the sniffing position. Mask ventilation operators will be confined to anesthesiology residents, Clinical anesthesiologist assistants (C-AA), and C-AA students all of whom are familiar with bag mask ventilation. Mask ventilation will occur using a two-handed Thenar-Eminence (TE) grip without the addition of an oropharyngeal airway. All operators will be instructed on how to perform this technique prior to patient enrollment. We will use Pressure Control ventilation mode on Anesthesia Ventilator machine (Dräger Perseus A500) set at 10 breathes per minute, I:E time of 1:2 and peak inspiratory pressure of 20 Cm H2O. An external pneumotachograph device and sensors (Phillips Respironics NM3™ respiratory profile monitor; Respironics CAPNOSTAT® Mainstream CO2 sensor) (figure1) will be used to measure ventilation parameters (Vtins; ml, VtExp; ml, PPins; cm H2O, Res; cm H2O/L/sec) with collected data electronically saved to a dedicated flash drive associated with the pneumotachograph.

Prior to induction airway operators (Clinical Anesthesiologist Assistants, Anesthesiology Residents or Anesthesiologist attendings) will be trained to create an opening in the Tegaderm™. The steps of Tegaderm™ modification are as follows: 1.) Tegaderm™ will be folded in half. 2.) Two 1" cuts will be made forming an Isosceles triangle. 3.) Tegaderm™ is opened up, placed on the patient with the adhesive side down. Once placed the covering's structural backing is removed so not to create any creases, leaving a diamond shaped mouth hole allowing face mask perimeter to make contact with Tegaderm™.

[figure not shown]

Figure 1: <https://www.zoll.com/medical-products/defibrillators/r-series/etco2/>

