Once standard ASA monitors are applied, an adult-sized oxygen mask (Medline™ Anesthesia Mask) will be placed over patient's face for pre-oxygenation with 100% O2 at a rate of 10 liters/minute until measured expired oxygen  $\geq 80\%$ . Immediately prior to administration of induction medications we will open the randomization envelope denoting which technique we will apply first. General anesthesia will be induced with 1–3 mcg/kg bolus of fentanyl, 1.5 mg/kg of lidocaine, 2–3 mg/kg propofol and 0.6–1mg/kg Rocuronium for ideal mask ventilation conditions. The study interval will be specified as the period beginning with apnea, anesthesia induction with neuromuscular

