## Tegaderm™ Placement for Bag Mask Ventilation in the Bearded Patient

blockade to completion of one minute of mask ventilation with and without Tegaderm™ use. Patients will act as their own controls. Anesthesia induction and apnea will be defined as no voluntary respiratory effort and the absence of the eyelid reflex. Complete Neuromuscular blockade will be defined as Train of Four Ratio of **0/4** with neuromuscular monitoring at the *Corrugator Supercilii* muscle.

Once subjects are apneic and induced, **3** mask ventilation breaths will be administered in order to ‘acclimate’ the user to the mask and insure a proper thenar-eminence (TE) grip is being used. The randomized crossover trial will be started once complete neuromuscular blockade is verified. Every consecutive trial will alternate between starting with Tegaderm™ use and no alteration with patients acting as their own controls. Both no alteration and Tegaderm™ portion of exam will use the Resironics NM3™ (Resironics Deutschland, Herrsching, Germany) and CAPNOSTAT® 5 (Phillips Healthcare corporation, Eindhoven, The Netherlands) sensors to measure primary outcomes: Inspired tidal volumes (  $V_{t_{ins}}$ ; ml ), expired Tidal Volumes of End Tidal CO2 (  $V_{t_{Exp}}$ ; ml ) which will be used to determine predefined adequate BMV (Inspired Tidal Volume- Expired Tidal Volume difference of <15% defined as adequate) and secondary outcomes: within-patient differences between Tegaderm™ and no-alteration conditions for peak inspiratory pressures (  $PP_{ins}$ ; cm H2O ) and airway resistance (  $Res$ ; cm H2O/l/sec ) for 60 seconds, and facial hair grouping comparisons. The anesthesia machine will be set to deliver standardized pressure-controlled ventilation using common parameters: peak inspiratory pressure of 20 cm H2O, 10 breaths per minute, and an inspiratory-expiratory ratio of 1:2. These values are within common ranges used in standard practice, but may be modified during surgery as determined to be clinically appropriate by the attending anesthesiologist. General anesthesia will be maintained with sevoflurane 4-6% with 100% O2 at a rate of 6 liters per minute. Once data is gathered for the first part of the trial (no alteration or Tegaderm™), we will change our technique and collect data for second 60 seconds component of the trial in similar fashion to initial data collection.

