If during the “no alteration” portion of the study we fail to establish a seal after 3 attempts at ventilation, an Attending Anesthesiologist would assess the stability of the patient and, if needed, attempt bag mask ventilation, incorporate airway adjuncts, and follow the difficult airway algorithm. If the patient is deemed stable a Tegaderm™ will be immediately applied over the patient’s face with a hole over the mouth. The same operator will perform TE grip MV technique in order to establish a seal and to collect our data. If a subject could not be rescue ventilated after application of Tegaderm™ placement, an Attending Anesthesiologist would follow the same rescue techniques as described above. Once the mask ventilation trial is completed, subjects will be intubated and maintained under general anesthesia as usual for their anticipated surgery.

In a hemodynamically unstable event the protocol will be halted in order to address the medical needs of the patient, the Attending Anesthesiologist would treat the event accordingly with the appropriate pharmacologic interventions. Once the patient is deemed medically stable the Attending Anesthesiologist would make the decision to

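### Section 3.2 conceals only the starting order: the seal behind the primary leak outcome is held by an operator who sees the dressing, may be a resident investigator and is not kept from the live NM3 volumes

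*Combined protocol and SAP*

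**What the plan says.** All references are to the combined protocol and SAP.

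- **Blinding.** Section 3.2, labelled as allocation concealment, says: "Providers and subjects will be blinded to which method they will start with". It does this by envelope, up to induction. Section 12.1 fixes when this ends: "Immediately prior to administration of induction medications we will open the randomization envelope denoting which technique we will apply first". Both measured windows come after that.
- **Outcome.** Section 7.1 defines the primary outcome as leak, computed from average inspired and expired volumes relative to the inspired volume and compared within patient. Section 13.1 analyses it as a paired difference.
- **Seal.** Under 3.4 and 12.1 the ventilator delivers the breaths at fixed pressure-control settings. The mask is held by hand with a two-handed thenar-eminence grip.
- **Operators and investigators.** Section 3.4: "Mask ventilation operators will be confined to anesthesiology residents, anesthesiologist assistants (AA), and AA students". Section 9.1: "Other investigators include experienced clinicians, a PhD research specialist, and medical residents". No sentence bars an investigator from holding the mask.
- **Live reading.** Sections 3.4 and 12.1 add the NM3 monitor for the study and save its data to a flash drive. The text does not say who may see the display during the windows.
- **Same operator.** The explicit statement concerns the path after a failed seal without the dressing: "The same operator will perform TE grip MV technique in order to establish a seal and to collect our data".
- **Operator data.** Section 12.2.2 lists the provider's level, but not whether that person is an investigator.

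**The concern.** A mask seal depends partly on how firmly and carefully someone holds the mask. Here that person knows the condition, may belong to the team testing the hypothesis, and may be able to watch the inspired and expired volumes and adjust the grip to them. If effort differs systematically between the two conditions, the difference enters the primary paired comparison and cannot be separated afterwards from what the dressing does.

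Two results depend on this. One is the estimate itself: section 2.3 describes existing evidence as anecdotal and hopes the study will inform guidelines. The other is the main-phase sample size, because section 13.2 takes the effect size from the 25-patient pilot. A bias in the pilot would carry into that calculation.

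**Working it through.** **No figure to reproduce.** The plan states no SD, effect size, power or alpha for leak (5.2 and 13.2 say the data for a power calculation are not available). The check is therefore a reading of the safeguards followed by an illustration.

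**Step 1: what each safeguard covers.**

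| Safeguard | Where | What it controls | Equalises grip effort between conditions? |
|---|---|---|---|
| Envelope | 3.2, 12.1 | Knowledge of the order, up to induction | No |
| Electronic recording | 3.4, 12.1 | Accuracy of the reading | No |
| Fixed ventilator settings | 3.4, 12.1 | Pressure, rate and I:E ratio delivered | No |
| One prescribed grip, with instruction | 3.4, 12.1 | Type of grip | Only in part |
| Three acclimation breaths | 12.1 | Grip before the first window | No |
| Patient as own control | 7.1, 13.1 | Differences between patients | No |

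**Step 2: why pairing and order do not help.** Write the within-patient difference as

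D = δ + b + (period effect, sign set by order) + error,

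where δ is the dressing's effect and b the shift from effort linked to the condition. Balanced order cancels the period term. It leaves b, because b follows the dressing and not the window. The mean of D therefore estimates δ + b at any sample size.

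This holds whether the order comes from the envelope or from the rule in 12.1 that "Every consecutive trial will alternate between starting with Tegaderm™ use and no alteration with patients acting as their own controls". A simulation with n = 25, SD 15, δ = 0, b = 5, a period term of ±2 and 20,000 runs gave:

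- random order: mean estimate 4.98, rejection 35.5%
- alternating order: mean estimate 4.93, rejection 35.0%

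The small shortfall under alternation is the 13-to-12 imbalance: 5 + (12×2 − 13×2)/25 = 4.92. The shift stays near 5 under both rules.

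**Step 3: illustration of size.** Assumptions, none of them from the documents: δ = 0, b = 3 percentage points, paired SD 10, 15 or 20 points, two-sided alpha 5%, paired t-test. The sample size n = 25 is the pilot in 5.2. The noncentrality is b√n/SD and the critical value is t(0.975, 24 df) = 2.064.

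| SD | Noncentrality | Rejection probability |
|---|---|---|
| 10 | 3×5/10 = 1.50 | 30% |
| 15 | 3×5/15 = 1.00 | 16% |
| 20 | 3×5/20 = 0.75 | 11% |

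The nominal rate is 5%. Because b is fixed while the standard error falls with √n, more patients raise these rates.

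**Step 4: direction.** The sign of b is not known. An operator who expects the dressing to work may relax without it. One who sees a large leak without it may grip harder, which makes the dressing look less effective. With a true 3-point benefit and an opposing 3-point shift, the expected difference is 3 − 3 = 0.

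**The case against.** The strongest reply is that no operator can be blinded to a dressing on the face, that nearly every manual-device crossover shares this limit, and that the plan already has objective recording, fixed settings and a prescribed grip. That stands as far as blinding goes. It does not reach the two things that can be changed: the operator's stake in the result and the live research reading.

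A second reply is that turning the NM3 away only partly shields the operator, because the ventilator's own readings remain visible and section 14.2 notes that the anesthesia record already holds ventilation parameters. That also stands. It is why the limitation must be reported as well as reduced.

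A reader might infer more than the documents support:

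- *That 3.2 claims to mask the condition.* It is labelled as allocation concealment and covers order only.
- *That investigators do hold the mask.* The two groups can overlap. No sentence says that they do.
- *That operators do watch the NM3.* The plan is silent, so what is missing is a safeguard.
- *That the mask-operator lists conflict.* Section 12.1 says "Prior to induction airway operators (Clinical Anesthesiologist Assistants, Anesthesiology Residents or Anesthesiologist attendings) will be trained to create an opening in the" dressing, and that list includes attendings and omits students. It concerns who is trained to cut the dressing. The same section opens with essentially the list in 3.4 for who holds the mask.
- *That the operator may change between windows.* The singular user in 12.1, the single provider level in 12.2.2 and the rule on the failed-seal path are most naturally read as one person throughout. A sentence for the ordinary path would be a clarification.
- *That a false positive for the dressing is shown to be likely.* The shift and the SD are assumed, the bias could run either way, and n = 25 is a pilot, not the confirmatory analysis.

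**Conclusion.** The concern holds as a gap in safeguards. Only the starting order is concealed, and only until just before induction. Part of the primary outcome then rests on the grip of an unblinded operator who may be an investigator and is not kept from the live NM3 volumes. Nothing in the design removes an effort difference tied to the condition.

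Neither the size nor the direction of any bias can be obtained from the documents. The 11% to 30% rejection rates rest wholly on a 3-point shift, a paired SD of 10 to 20 points and a two-sided 5% test, all assumed. They show that a modest shift would matter, not that this trial has one. This is a cheap improvement worth making before more patients are enrolled, and it does not invalidate the design.

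**What to change.** 1. **Section 3.4.** State that the person holding the mask in the two measured windows is not a study investigator.
2. **Section 12.1.** State that the added research NM3 display faces away from that person during both windows, that all routine anesthesia monitors stay in view, that the supervising attending sees everything including the NM3, and that every rescue provision is unchanged.
3. **Reporting.** State as a limitation that the operator was not blinded to the dressing and could still see the ventilator's own readings.
4. **Optional.** Add a sentence to 12.1 that the same person holds the mask in both windows on the ordinary path.

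The cost is protocol wording and the position of one screen, with a slightly smaller pool of operators per case. No extra patients, staff or procedures are needed.
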